6.2 Study Population

6.2.1 Disposition of Participants

The following participant data will be presented:

Analysis population: All participants who complete double blind part, Analysis group: ASP0367 any dose group, Placebo to ASP0367 group and Total

- Number and percentage of participants who were administered at least one dose of study drug during the OLE part,
- Number and percentage of participants who completed and those who discontinued the treatment during the OLE part, by primary reason for treatment discontinuation,
- Number and percentage of participants who completed and those who discontinued the follow-up period, by primary reason for follow-up discontinuation.

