4.1 Safety Analysis Set

The SAF consists of all participants who receive at least 1 dose of ASP0367. The SAF only includes participants who were randomly assigned to ASP0367 in DB part or participants who were randomly assigned to placebo in the DB part and continued into the OLE part. Participants who were randomly assigned to placebo and discontinued the study in the DB part are not included in the SAF, even if they erroneously received ASP0367 during the DB part.

The SAF will be used for all summaries of the safety data.

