6 STATISTICAL METHODOLOGY

6.1 General Considerations

Continuous data will be summarized descriptively including the number of participants (n), mean, standard deviation (SD), median, minimum and maximum. Categorical data will be summarized by frequencies and percentages. Percentages by categories will be based on the number of participants with no missing data, i.e. the percentages for the non-missing categories will add up to 100%.

There are 2 different groups defined based in the randomization group:

- ASP0367 any dose group: Participants randomly assigned to ASP0367.
- Placebo to ASP0367 group: Participants randomly assigned to placebo and who continue into the OLE and receive ASP0367.

Safety analysis and other summaries based on SAF will be presented by analysis group (ASP0367 any dose group or Placebo to ASP0367 group), unless specifically stated otherwise.

All data summarization and analyses will be performed using SAS® Version 9.4 or higher on Linux. Specifications for table, figures, and data listing formats can be found in the TLF specifications.

For continuous variables that are recorded as "<X", "<=X", ">X", or ">=X", the value of "X" will be used in the calculation of summary statistics if otherwise noted. This approach may result in a summary that reflects the presence of an analyte (such as troponin) when in fact the analyte was not detected but reported as less than the lower limit of detection by the assay.

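### In the 76-week SAP's disposition table, the placebo column contains only participants already dosed in the OLE, so its OLE uptake is 100% by construction and placebo completers who were not dosed have no column

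*SAP*

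**What the plan says.** Section 6.2.1 of the 76-week SAP (the plan covering the double-blind and OLE parts) gives the population and columns of its disposition table: "Analysis population: All participants who complete double blind part, Analysis group: ASP0367 any dose group, Placebo to ASP0367 group and Total". The first row is "Number and percentage of participants who were administered at least one dose of study drug during the OLE part". The other rows give completion and discontinuation of OLE treatment, and completion and discontinuation of follow-up, each with the primary reason.

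Section 6.1 of the same SAP supplies the column definitions. It states "There are 2 different groups defined based in the randomization group" and lists them. The first, the any-dose group, is simply everyone randomised to active drug. The second is narrower, and its entry reads: "Placebo to ASP0367 group: Participants randomly assigned to placebo and who continue into the OLE and receive ASP0367".

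The active group carries no OLE condition. The placebo group carries two: entering the OLE and receiving ASP0367. No other section redefines the placebo group for the disposition table, and none says who is counted under Total.

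Section 4.1 limits the Safety Analysis Set (SAF) in a similar way. Placebo participants enter it as "participants who were randomly assigned to placebo in the DB part and continued into the OLE part".

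Section 6.2.1 of the 52-week SAP reports disposition for all randomised participants, with a true placebo column. It covers completion and discontinuation of treatment and of study within the double-blind period, with no row for OLE entry.

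**The concern.** A table of OLE uptake among double-blind completers should show how many in each randomised group went on to the OLE. Here the placebo column is conditioned on the outcome that its first row is meant to measure. Read side by side, the two columns could suggest better uptake after placebo than after ASP0367 when the difference comes only from the definition. The group columns would also fail to add up to the stated population if any placebo completer was not dosed. A reader of the 76-week report uses this table to see how the Placebo to ASP0367 group came about, and as written the table cannot show that.

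**Working it through.** The plan states no figure on this point, so there is none to reproduce. The check sets the definitions against the population and then illustrates the effect.

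**Notation**

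- P = placebo-randomised double-blind completers
- k = those of P not dosed in the OLE
- A = ASP0367-randomised double-blind completers
- a = those of A dosed in the OLE

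**Placebo column.** The 6.2.1 population restricted to the 6.1 placebo group leaves P − k participants. The first-row numerator, those dosed in the OLE, is also P − k. The percentage is (P − k)/(P − k) = 100% for every k below P.

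**ASP0367 column.** The group has no OLE condition, so the percentage is a/A, which can take any value from 0% to 100%.

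**Participants in neither column.** The population is A + P. The two columns sum to A + P − k, so k participants are in the population but in no group.

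**Total.** If Total is the sum of the columns, its uptake is (a + P − k)/(A + P − k). If it is all completers, its uptake is (a + P − k)/(A + P). The SAP does not say which.

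**Illustration.** The documents give no count of completers or of non-entrants. Assume 33 participants (the number in the interim analysis), an exact 1:1:1 split, all completing the double-blind part, and all active completers dosed. Then P = 11 and A = a = 22. A second case takes P = 8, also an assumption.

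| k | Placebo uptake as written | (11 − k)/11 | (8 − k)/8 |
|---|---|---|---|
| 0 | 100% | 100% | 100% |
| 1 | 100% | 90.9% | 87.5% |
| 2 | 100% | 81.8% | 75.0% |
| 3 | 100% | 72.7% | 62.5% |

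With P = 11 and k = 2, the columns sum to 22 + 9 = 31 of 33. Total uptake is 31/31 = 100% under one reading and 31/33 = 93.9% under the other.

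**Other tables in the same SAP.** Protocol deviations (6.2.2) use randomised participants who took ASP0367, and demographics (6.2.3) use the SAF. Both populations fit the two groups. The mismatch arises in 6.2.1, which pairs a wider population with the OLE-conditioned placebo group.

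**Recovery from the other SAP.** The 52-week table gives placebo completers (P), and the 76-week table gives placebo participants dosed in the OLE (P − k). Dividing the second by the first gives the uptake, 9/11 = 81.8% in the example. This requires both SAPs to count completers in the same way.

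**Follow-up rows.** The 76-week follow-up row covers double-blind completers only, and the 52-week disposition rows stop at the double-blind period. Neither SAP therefore lists follow-up completion for ASP0367-randomised participants who stopped in the double-blind part.

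**The case against.** The strongest reply is that this is a label and not a rule. Section 6.1 ties presentation by the two groups to SAF-based summaries, and the disposition table is not one of them. Table shells are in separate specifications that are not part of these documents. A sensible programmer would treat Placebo to ASP0367 as a sequence label and use all placebo completers as the denominator, because the uptake row is empty of meaning otherwise. It is true that the delivered table may come out right. But 6.2.1 names a group that 6.1 defines explicitly, and using a different denominator would depart from the written definition.

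A second reply is that little depends on the table, and this stands. The information is not lost, because uptake can be recovered as shown above. If Total means all completers, the non-entrants also appear as Total minus the two columns. No document says that any placebo completer failed to enter the OLE.

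A reader might infer that the 76-week safety comparison is distorted, with switchers set beside continuers and the selection hidden for one side. The documents do not support that. The ASP0367 group in the SAF is everyone randomised to ASP0367, including those who stopped in the double-blind part, so OLE uptake does not measure selection into it. The safety tables use the SAF, whose definition does not depend on 6.2.1.

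A reader might also infer that about one in ten ASP0367 participants goes unaccounted for. That would borrow the 10% drop-out assumed in sizing the 24-week design and apply it to a 52-week double-blind part. It would also overlook that these participants' treatment and study discontinuation is reported under the 52-week SAP. Only a follow-up-completion row is absent for them.

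**Conclusion.** The point holds as a conflict between two stated definitions. Under the written rules the placebo uptake percentage is fixed at 100%, any placebo completer not dosed in the OLE belongs to the population but to neither column, and Total is undefined. This part needs no numerical assumption.

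Its practical size is small and cannot be fixed from the documents. It is nil if k = 0. In the illustration, one to three non-entrants among 11 placebo completers would put true uptake between 90.9% and 72.7% against a displayed 100%. No estimate, test or SAF-based safety summary changes. It is a minor correction to a descriptive table.

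**What to change.** In Section 6.2.1 of the 76-week SAP, for this table only:

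- Define the columns by randomised double-blind treatment: ASP0367 any dose, and placebo.
- Use all double-blind completers in each column as the denominator for the OLE rows.
- Define Total as all double-blind completers.

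Keep Placebo to ASP0367 as the group for the SAF-based tables. Optionally, add a follow-up-completion row for ASP0367-randomised participants who stopped in the double-blind part.

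The cost is a few lines of SAP text and a changed column definition in one table, with no new data. If the SAP can no longer be revised, the change can be recorded in the clinical study report, as Section 1 of the 76-week SAP provides for changes from the planned analyses that affect the statistical analyses.

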6.2.2 Protocol Deviations

Analysis population: All randomized participants who took ASP0367, Analysis group: ASP0367 any dose group, Placebo to ASP0367 group and Total

The number and percentage of participants with the following protocol deviation criteria (defined as an important protocol deviation) will be summarized for each criterion and overall, by treatment group and total as well as by investigative site. Participants deviating from a criterion more than once will be counted only once for the corresponding criterion.

The unique identifiers will be as follows:

PD1 - Inclusion/Exclusion,

PD2 - Withdrawal Criteria,

PD3 - Study Intervention,

PD4 - Excluded Concomitant Medications,

PD5 - Informed Consent,

PD6 - Safety Reporting, and

PD7 - Procedures/Tests

6.2.3 Demographic and Other Baseline Characteristics

Analysis population: SAF, Analysis group: ASP0367 any dose group, Placebo to ASP0367 group and Total

• Demographic and other baseline characteristics (age, sex, race and ethnicity, body weight, height and BMI) will be summarized by descriptive statistics and frequency tabulations [Table 1].

Table 1 Demographic and baseline characteristics

Item	Classification
Sex	1: Male
	2: Female
Age (Years) [Informed Consent]	Measurement value
Age	1: >=18 to <65
8	2: >=65 to <=80
Ethnicity	1: Not Hispanic or Latino
	2: Hispanic or Latino
Race	1: White
	2: Black or African American
	3: Asian
	4: American Indian or Alaska Native
	5: Native Hawaiian or Other Pacific Islander
	6: Other
Height (cm) [Screening]	Measurement value
Weight (kg) [Screening]	Measurement value
BMI (kg/m^2) [Screening]	Measurement value
BMI	1: < 25
	2: >=25
Site Group	1: Mayo clinic Minnesota
•	2: Non-Mayo clinic Minnesota
Walking aid use [Baseline [†]]	0: No
	1: Yes
Duration of disease (Years) [‡]	Measurement value
Treated with medication [Screening]	0: No
	1: Yes
Syndrome	1: Kearns Sayre Syndrome (KSS)
	2: Mitochondrial Encephalomyopathy, Lactic Acidosis and
	Stroke-like episodes (MELAS)
	3: Maternally Inherited Diabetes Deafness (MIDD)
	4: Myoclonic Epilepsy with Ragged Red Fibers (MERRF)
	5: Chronic Progressive Externa Ophthalmoplegia (CPEO)
	6: 3-methylglutaconic aciduria, Deafness, Encephalopathy,
	and Leigh-like disease (MEGDEL)
	7: Leigh Syndrome
	8: Multisystem mitochondrial disorder
	9: Mitochondrial Myopathy
	10: POLG-related disorders
	11: Others
Genetic abnormality	1: Mitochondrial DNA
NO. 1 11 IDAY	2: Nuclear DNA
Mitochondrial DNA mutant heteroplasmy	0: No
information is available	1: Yes
Level of heteroplasmy (%)	Measurement value

BMI: body mass index; CPEO: Chronic Progressive Externa Ophthalmoplegia; KSS: Kearns Sayre Syndrome;

MEGDEL: 3-methylglutaconic aciduria, Deafness, Encephalopathy, and Leigh-like disease; MELAS: Mitochondrial Encephalomyopathy, Lactic Acidosis and Stroke-like episodes; MERRF: Myoclonic Epilepsy with Ragged Red Fibers; MIDD: Maternally Inherited Diabetes Deafness; POLG: polymerase-gamma.

†: For participants received ASP0367 on double blind part, the measurement at week 0 will be used as baseline, and for participants received placebo on double blind part, the measurement at week 52 will be used as baseline.

‡: Duration of disease will be calculated as follows:

[("Date of First Study Drug Taken" – "Date of Diagnosis") + 1] / 365.25.

If Date of Diagnosis is missing or incomplete, then impute the date following the rule stated in [Section 6.8.2].

6.3 Study Drugs Exposure and Compliance

Analysis population: SAF, Analysis group: ASP0367 any dose group or Placebo to ASP0367 group

• The duration of ASP0367 exposure for each participant will be summarized by descriptive statistics and frequency tabulations. The following categories of the duration of exposure (days) will be defined:

```
< 29 (4 weeks)

>= 29 (4 weeks) to < 85 (12 weeks)

>= 85 (12 weeks) to < 169 (24 weeks)

>= 169 (24 weeks) to < 253 (36 weeks)

>= 253 (36 weeks) to < 365 (52 weeks)

>= 365 (52 weeks) to < 449 (64 weeks)

>=449 (64 weeks) to <533 (76 weeks)

>=533 (76 weeks)
```

The duration of ASP0367 exposure will be calculated as follows: {"Date of Last Study Drug Taken" – "Date of First ASP0367 Taken*"} + 1.

Date of Last Study Drug Taken is defined as the latest date of ["Date of Last Study Drug Taken (Phase 2 Treatment Period)", "Date of Last Study Drug Taken (Dose selection Period)", or "Date of Last Study Drug Taken (Open-Label Extension Part)"].

- *: For participants received ASP0367 on double blind part, "Date of First Study Drug Taken" will be used. For participants received placebo on double blind part, "Date of First Study Drug Taken (Open-Label Extension Part)" will be used.
- The compliance of ASP0367 exposure for each participant will be summarized by descriptive statistics and frequency tabulations. The following categories of the study drug compliance (%) will be defined:

```
    < 50

    >= 50 to < 75

    >= 75 to < 90

    >= 90
    Unknown
```

The compliance of study drug exposure for ASP0367 any dose group will be calculated as follows:

Total number of dispensed tablets of ASP0367 - Total number of returned tablets of ASP0367 ×100

The number of tablets of ASP0367 to be taken

The number of tablets to be taken is defined as follows;

[{"Date of Last Study Drug Taken" – "Date of First Study Drug Taken"} + 1] x the number of tablets per day.

The compliance of study drug exposure for Placebo to ASP0367 arm will be calculated as follows:

Total number of dispensed tablets in OLE part - Total number of returned tablets in OLE part

The number of tablets to be taken in OLE part

The number of tablets to be taken in OLE part is defined as follows;

["Date of Last Study Drug Taken (Open-Label Extension Part)" – "Date of First Study Drug Taken (Open-Label Extension Part)" + 1] x the number of tablets per day.

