4.2.1 Summary of Changes to Study Design

The present study was originally designed as a randomized, double-blind, placebo-controlled, oral dose, adaptive phase 2/3 study with open-label extension (OLE) to evaluate the efficacy,

safety and tolerability of ASP0367 in participants with PMM. The original study design consisted of the following portions: screening (4 weeks); phase 2 dose selection portion with 2 doses of ASP0367 vs matching placebo (2 weeks); phase 3 portion with selected, single dose treatment vs placebo (up to 52 weeks); OLE (24 weeks); and follow-up (4 weeks).

Effective with implementation of Protocol Version 9.0 (Substantial Amendment 8), the original study design will be modified to become a phase 2 study (originally referred to as the "Phase 2 Portion") with a double-blind treatment period (24 weeks) and no OLE period. An interim analysis of approximately 30 evaluable participants who have reached week 24 of the double-blind treatment period will be conducted to evaluate futility and efficacy.

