6.3 Study Drugs Exposure and Compliance

Analysis population: SAF, Analysis group: ASP0367 30 mg group, ASP0367 75 mg group, ASP0367 any dose group or placebo group

- The duration of study drug exposure for each participant in double blind part will be summarized by descriptive statistics and frequency tabulations. The following categories of the duration of exposure (days) will be defined:
 - \circ < 29 (4 weeks)
 - \circ >= 29 (4 weeks) to < 85 (12 weeks)
 - \circ >= 85 (12 weeks) to < 169 (24 weeks)
 - \circ >= 169 (24 weeks) to < 253 (36 weeks)
 - $\circ >= 253 (36 \text{ weeks}) \text{ to } < 365 (52 \text{ weeks})$
 - $\circ >= 365 (52 \text{ weeks})$

The duration of study drug exposure in double blind part will be calculated as follows: {"Date of Last Study Drug Taken in double blind part" – "Date of First Study Drug Taken"} + 1.

Date of Last Study Drug Taken in double blind part is defined as the latest date of ["Date of Last Study Drug Taken (Phase 2 Treatment Period)" or "Date of Last Study Drug Taken (Dose selection Period)" or "Date of Last Study Drug Taken (Phase 3 Treatment Period)"].

- The compliance of study drug exposure for each participant in double blind part will be summarized by descriptive statistics and frequency tabulations. The following categories of the study drug compliance (%) will be defined:
 - o < 50
 - \circ >= 50 to < 75
 - \circ >= 75 to < 90
 - $_{\circ} >= 90$
 - Unknown

The compliance of study drug exposure in double blind part will be calculated as follows:

Total number of dispensed tablets - Total number of returned tablets in double blind part

The number of tablets to be taken in double blind part

The number of tablets to be taken in double blind part is defined as follows:

[{"Date of Last Study Drug Taken in double blind part" – "Date of First Study Drug Taken"} + 1] x 3.

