1 INTRODUCTION

This SAP contains technical and detailed elaboration of the principal features of the analysis described in the protocol and includes procedures for executing the statistical analysis to fulfil the objectives of the study.

The study was designed to be, and executed as, a double-blinded with an OLE. The OLE was removed from protocol version 9.0 and so the use of the present tense is no longer accurate. In addition to the objectives and endpoints defined in Study 0367-CL-1201 protocol (core protocol), some additional objectives and endpoints specific to the Mayo Clinic (Minnesota) had been defined in Study 0367-CL-1201 [MAYO] Protocol. However, as there have been no participants recruited to the protocol from the Mayo sites, therefore there will be no SAP created. Until protocol version 7.0, the double-blinded period was 52 weeks and open label extension period was 24 weeks. However, from protocol version 8.0 onwards, the doubleblinded period was revised to 24 weeks and in protocol version 9.0 the OLE period was removed. Since no participants have been evaluated under protocol version 8.0 or later, two SAPs will be prepared: one for analyses up to 52 weeks of treatment (the double-blind part of the study), and the other one for analyses at the end of 76 weeks of treatment (the doubleblind part and the OLE part of the study). In this analysis, participants assigned ASP0367 in the double-blinded period will be analyzed for through the double-blinded part and the OLE part of the study including follow-up visit, while participants switched from Placebo to ASP0367 in the OLE part will be analyzed in the OLE part only including follow-up visit. This document is an analysis plan for the up to 76 weeks (double-blinded part and OLE part of the study) including follow-up visit.

Analyses for pharmacokinetic and pharmacodynamic (target gene expression and biochemical markers) endpoints, including exposure-response assessment, will be described in the separate analysis plan and this SAP only focus on safety endpoints.

This document will be finalized prior to the database lock at the end of study. If there are any changes from the planned analyses in the final version of the SAP that impact the statistical analyses, then it will be documented in the CSR.

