5.2 Safety Endpoints

5.2.1 Treatment Emergent Adverse Events (TEAEs)

AE collection begins after the ICF has been signed and continues until the follow up visit or 28 days after the final IP administration or when the participant is determined to be a screen failure. A TEAE is defined as an AE observed after starting administration of the ASP0367 to 28 days after the last dose of ASP0367.

An IP-related TEAE is defined as any TEAE with a causal relationship of "yes" by the investigator.

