5.2.2 Vital signs

Vital signs including blood pressure, pulse rate and body temperature will be assessed at each visit scheduled in the protocol.

5.2.3 12-lead Electrocardiogram (ECG)

- A standard 12-lead ECG will be conducted using both a central ECG reading laboratory and local ECG reading. ECGs at weeks 2 and 8 will be performed at the participant's home by a qualified healthcare provider from the home healthcare vendor. In case the home healthcare visit is not feasible, the visit can be conducted at the study site.
- ECGs will be recorded in triplicate (3 separate ECGs, 5 minutes resting prior to first ECG and at least 1 minute apart per time point), prior to blood draw and transmitted electronically for central reading. The mean of the triplicate ECG from central and local read should be used for treatment decisions and AE reporting.
- If the mean triplicate QTcF is > 500 msec at any time point, one follow-up triplicate ECG may be performed on the same day. If the follow-up mean QTcF is ≤ 500 msec, the participant may proceed with IP. If the follow-up mean QTcF > 500 msec is confirmed, then the participant must discontinue IP.
- An ECG will also be performed within 24 hours of any of these events: an elevation of cTnI above the ULN (see Appendix 10.9 in the protocol for reference range), or when there is an elevation of cTnT above the ULN (see Appendix 10.9 in the protocol for reference range) or above the participant's baseline value if it was elevated, or when a participant has any signs or symptoms reflecting cardiac involvement, inclusive of new onset shortness of breath. If the ECG is within normal limits, a repeat of the abnormal troponin value (cTnI or cTnT) should be obtained. For any of the situations above, it

may be required to interrupt or discontinue further administration of IP. Participants with persistent cTnI or cTnT elevations, abnormal ECG or abnormal echocardiogram should undergo cardiology follow up.

The requirement to perform an ECG after elevations observed in Troponin T was not added to the protocol until version 9.0. Therefore, this ECG requirement related to cTnT elevation was not implemented as all participants enrolled under and participated in the protocol version 7.0 or earlier.

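### The 76-week SAP leaves the Phase 3 Treatment Period out of its last-dose rule, while the 52-week SAP includes it; exposure and compliance would be wrong for any ASP0367 participant whose last dose is recorded there and who did not enter the extension

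*SAP*

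**What the plan says.** Two SAPs carry the date 9 July 2024: version 3.0 for the 52-week double-blind part and version 1.0 for the 76-week analysis (section 7 of each).

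- **52-week SAP, section 6.3.** The last double-blind dose is the latest of the Phase 2 Treatment Period, Dose selection Period and Phase 3 Treatment Period dates. The third is listed explicitly: "Date of Last Study Drug Taken (Phase 3 Treatment Period".
- **76-week SAP, section 6.3.** The last dose is the latest of the Phase 2 Treatment Period date and two others: "Dose selection Period)', or 'Date of Last Study Drug Taken (Open-Label Extension Part". There is no Phase 3 Treatment Period date and no reason is given.
- **Scope of the 76-week SAP.** Section 1 says that "participants assigned ASP0367 in the double-blinded period will be analyzed for through the double-blinded part" and the extension. For those randomized to ASP0367, the safety set in section 4.1 does not require entry into the extension: "The SAF only includes participants who were randomly assigned to ASP0367 in DB part", together with placebo participants who continued into the extension.
- **Original design.** Protocol section 4.2.1 describes a "phase 3 portion with selected, single dose treatment vs placebo (up to 52 weeks" that came before the extension. Section 5.2.3 of the 76-week SAP says that "all participants enrolled under and participated in the protocol version 7.0 or earlier".

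**The concern.** The 76-week SAP covers all double-blind dosing of the ASP0367 participants plus the extension. Its list of dates should therefore be the three double-blind dates plus the extension date. Instead, the extension date stands where the Phase 3 date stood.

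Section 6.3 uses this date directly for exposure duration and for the compliance denominator of the any-dose group. It is also the only definition of the last dose in that SAP, so a programmer would naturally use it for:

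- the treatment-emergent window, "28 days after the last dose of ASP0367" (section 5.2.1);
- the laboratory and liver threshold windows (sections 6.5.2 and 6.5.2.1);
- the 7-day cut for all visits except follow-up, and the follow-up window itself (section 6.8.1).

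Any error goes one way. A maximum taken over fewer dates can only be earlier, so exposure can only be understated, compliance overstated, and on-treatment safety data lost. The two SAPs could also give the same person different last double-blind doses.

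**Working it through.** The plan states no figure to reproduce here; the check applies its formulas to assumed dates.

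**Who could be affected.**
- ASP0367-randomized, last dose in the Phase 3 period, no extension: affected.
- Entered the extension, including Placebo to ASP0367: not affected, because the extension date is the latest.
- Placebo, stopped in the double-blind part: not in the 76-week safety set (section 4.1).

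**Formulas (76-week SAP).**
- Exposure = last dose − first ASP0367 dose + 1 (section 6.3).
- Compliance, any-dose group = 100 × (dispensed − returned) / [(last dose − first dose + 1) × tablets per day] (section 6.3).
- Visit cut = last dose + 7; treatment-emergent and laboratory windows = last dose + 28; follow-up window = last dose + 28 to + 35.

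**Inputs.** Three tablets a day (Protocol Table 5). Assumed: first dose day 1, every tablet taken, latest date in the Phase 2 or Dose selection fields day 168, true last dose in the Phase 3 period day 300, no extension.

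| Quantity | 76-week rule as written | With the Phase 3 date |
|---|---|---|
| Exposure | 168 − 1 + 1 = 168 days | 300 − 1 + 1 = 300 days |
| Compliance | (300 × 3)/(168 × 3) = 900/504 = 179% | 900/900 = 100% |
| Visit cut | 168 + 7 = day 175 | 300 + 7 = day 307 |
| Treatment-emergent and laboratory windows end | 168 + 28 = day 196 | 300 + 28 = day 328 |
| Follow-up window | days 196 to 203 | days 328 to 335 |

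The first two rows follow directly from section 6.3. The last three hold only if the section 6.3 date is the one meant by last dose.

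- The loss is 328 − 196 = 132 days of adverse event follow-up.
- In the exposure table the participant moves from the 253-to-364-day category to the 85-to-168-day category.
- The analysis windows for weeks 28, 32, 36 and 40 (days 183 to 294) fall wholly in the discarded stretch.
- The compliance frequency table would not show the problem, because its top category is open-ended at 90% or more. Only the maximum in the descriptive statistics would.

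**Range over assumed dates.** Earlier-period last doses on days 14, 84, 168 and 252 were crossed with true last doses on days 200, 300 and 364, keeping pairs where the true date is later.
- Days lost: from 200 − 168 = 32 to 364 − 14 = 350.
- Compliance: from 300/252 = 119% to 364/14 = 2600%.
- The day-14 cases follow the 2-week phase 2 portion in Protocol section 4.2.1. They also require no later Dose selection Period date, so they are the extreme end.

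A participant with only a Phase 3 date would have no last-dose date at all.

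**The case against.** The strongest reply is that the Phase 3 field may be empty. The phase 3 portion was to use one selected dose, and no document reports that a dose was selected. The 52-week SAP (section 6.1) keeps separate 30 mg, 75 mg and placebo groups with no selected-dose group. The internal committee recommended stopping for futility after the analysis of the first 33 participants (section 6.7.1). The 52-week SAP is the third version of a document first finalized in 2020, so its Phase 3 term could be a harmless leftover, and the newer 76-week SAP could have dropped it on purpose.

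This stands as a limit on the effect; it does not explain the text. Participants were under version 7.0 or earlier, and until version 7.0 the double-blind part lasted 52 weeks (section 1 of both SAPs). Late double-blind doses had to be recorded somewhere, and neither SAP maps the three fields to weeks. A reader cannot tell a deliberate omission from a slip.

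A second reply also stands in part. The 28-day windows refer to the last dose of ASP0367 without citing section 6.3. Read literally, that is the actual last dose, and nothing is lost. The 7-day cut is tied by name to the defined date only in the estimand table, which concerns the week-24 walk test, and this SAP runs no efficacy analysis.

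A reader might infer that participants who stop early mostly do so for safety reasons, so that the lost data are the most important. The documents give no reasons for stopping and do not support that.

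**Conclusion.** The two last-dose rules disagree, and the 76-week rule is incomplete for the dosing that it covers. Whether any result changes depends on a fact that the documents do not give: whether any ASP0367-randomized participant has a last dose recorded in the Phase 3 Treatment Period and no extension dose. If so, exposure and any-dose compliance are wrong for that person as section 6.3 stands. The adverse event, laboratory, visit and follow-up windows are wrong as well if they use the same date. The size is individual: 132 days and 179% compliance in the main illustration, and 32 to 350 days over the assumed combinations.

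A reader might go further and conclude that the 76-week exposure and safety summaries are in error. The documents do not support that, because no participant is shown to have a Phase 3 date. No efficacy result or placebo comparison in the 76-week analysis depends on it.

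**What to change.** In section 6.3 of the 76-week SAP, add the Phase 3 Treatment Period last-dose date to the list whose maximum defines the last study drug date, so that the two SAPs agree on double-blind dosing. Alternatively, state that no participant has such a date and reconcile section 6.3 of the 52-week SAP. In either case, state that this date is the last dose used for the treatment-emergent, laboratory, liver, visit and follow-up windows.

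The cost is one term in a definition, one sentence on the windows and one variable in the derivation program. A count of non-missing Phase 3 dates shows whether the change matters. If the field is empty, adding it changes nothing; if it is not, the change restores the correct exposure, and the safety data wherever the windows use that date.
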